#### 9.4 CT Scan Procedures

Study eligibility intracranial hemorrhage volume will be estimated by clinical and/or research staff using the ABC method. Subsequently, intracranial hemorrhage and edema volumes will be determined by a neuro-radiologist blinded to clinical data and SENSE device data. Quantification of volumes will be performed using computer-assisted methods. The blinded evaluator will be required to place seed-points within the volume of interest and adjust lower and upper intensity Hounsfield unit (HU) thresholds until the entire volume is correctly selected. In cases where the ICH volume cannot be differentiated from intraventricular hemorrhage (IVH) volume, the blinded evaluator will use freehand drawing tools in order to remove the IVH volume using his/her best

---

estimate. In this situation, the IVH will be determined using the original over-segmented volume that includes the combined ICH and IVH volumes,  $V_{total}$ , as  $IVH = V_{total} - ICH$ . This limitation is unavoidable as IVH has the same intensity as ICH and the two volumes often border each another. The volume (mL) and the affected part(s) of the brain will be measured from the segmented volume. Based on prior experimentation, it is anticipated there will be more difficulties in segmenting edema volumes as edema has more subtle HU intensity differences relative to normal tissue. Thus, edema segmentation will likely require more blinded evaluator effort (i.e., seed-points, freehand tools, etc.) The radiology report will be filed in the source documents for the study.

## 9.5 Study Evaluations

### 9.5.1 Pre-Monitoring Evaluations

These evaluations occur prior to the subject beginning study monitoring.

**Screening:** A history and physical examination will be performed by the treating physician, and routine evaluations (including a diagnostic head CT) and treatments for ICH will be performed in accordance with the institution's standard evaluation and treatment protocols and at the treating physician's discretion as deemed medically necessary. Screening will include completion of the NIH Stroke Scale and Glasgow Coma Scale.

**Enrollment:** If the diagnostic head CT is performed within 24 hours from ICH symptom onset, the patient will be evaluated for eligibility for the study. Informed consent will be obtained from the patient (if able) or surrogate (patient's next of kin or legal guardian).

### 9.5.2 Study Evaluations

The following study procedures will be performed at each of the following time points. If it is not possible to perform a measurement or examination due to the subject's condition or other reasons, the reason for not performing the test or measurement should be documented on the source documents.

- **Baseline:**

- A **first** study head CT will be performed on every study subject immediately prior to initiation of SENSE device monitoring.
- NIH Stroke Scale
- Glasgow Coma Scale
- SENSE device measurements within 15 minutes of **first study** head CT

- scan, or as soon as practicable
- Adverse event assessment
- **12 Hours (±6 hours):**
  - A standard of care head CT will be performed at 12 (±6) hours from first study CT to evaluate for hemorrhage expansion
  - NIH Stroke Scale
  - Glasgow Coma Scale
  - SENSE device measurements within 15 minutes of head CT scan, or as soon as practicable for continuous monitoring, or every 6 (±1) hours for intermittent monitoring
  - Adverse event assessment
- **72 Hours (±12 hours):** A study CT will be performed at 72 (±12) hours to evaluate cerebral edema.
  - NIH Stroke Scale
  - Glasgow Coma Scale
  - SENSE device measurements within 15 minutes of before or after head CT scan, or as soon as practicable
  - Adverse event assessment
- **7 days:** Adverse event assessment. After the subject is discharged from the hospital or through 7 days of hospital stay (whichever occurs first), the subject's inpatient medical records will be reviewed to detect any device related adverse events or epileptic seizures that may have emerged after the SENSE headset was removed.
- **6 weeks (±2 weeks):** A phone call with the patient or surrogate will be completed at 6 (±12) weeks to capture the presence or absence of adverse events that may have emerged after completion of the 72-hour SENSE device measurement period.

Changes from the screening or baseline medical history and concomitant medications should be recorded in the source documents. Changes that could affect the SENSE measurements or CT results should be recorded on the case report forms (CRFs), including head movements that may affect positioning of the SENSE device.

Other tests or measurements, including routine EEGs and head MRIs, may be performed as needed for management of the subject's medical condition(s) per ICH standard of care. Subjects undergoing continuous EEG monitoring without resumption of SENSE monitoring, or a neurosurgical procedure before study completion will be terminated

---

 SENSE device measurements may be obtained prior to first study head CT scan if there is a scheduling delay between informed consent and first study head CT.

early from the study (see Section 9.10, Early Termination). Subjects may also be terminated early from the study if the SENSE device interferes with another monitoring device or the subject requires placement of a monitoring device that interferes with the SENSE device or headset, and the interference cannot be resolved or SENSE monitoring cannot be resumed. Whenever practicable, any subject who is terminated early and was exposed to the SENSE device should have the Day 7 and 6 week safety evaluations performed to capture any adverse events that emerged after device exposure.

The results of non-study diagnostic tests (except MRI) will not be recorded on the CRFs. Non-study tests relevant to an adverse event will be included in the investigator's adverse event summary on the adverse event CRF. The results of any non-study head MRI will be recorded on the MRI CRFs for clinical comparison with the CT scans.

### 9.5.3 Adverse Events and Device Malfunctions

Adverse events and device malfunctions will be assessed at study entry and at the baseline, 12 hour, 72 hour and 6 week evaluation time points. If it is anticipated that a subject will die or be taken for a neurosurgical procedure before the 12 hour CT scan, the scan will be performed earlier if practicable and used to judge hemorrhage. If it is anticipated that a subject will be discharged from the hospital, die, or undergo a neurosurgical procedure after the 12 hour CT scan but before the 72 hour scan, the 72 hour scan will be performed earlier if practicable and used for analysis.

During the 72 hours of monitoring, adverse events of particular interest for this first-in-man study in an ICU setting include:

- Adverse tissue reactions from the headset, such as skin irritation, abrasion or other dermatological effects
- Discomfort of the head or neck from the headset
- Seizures (defined as clinical tonic-clonic activity that occurs during the 72 hours of SENSE monitoring)

Device malfunctions will also be assessed for the SENSE device. Such malfunctions could include:

- Failure of the device to operate
- Operator errors
- Interference with other devices, including SENSE device interference with other monitors (e.g., ICP monitor dislodges) or other monitor (e.g., intraventricular catheter placement) interferes with SENSE device monitoring or headset placement

## 9.6 Post-Study Procedures

Subjects will be discharged from the SENSE monitoring part of the study after the final

72 hour CT scan and SENSE measurements are complete. After completion of these 72 hour evaluations, all other management of the subject's medical condition(s) will be per ICH standard of care. Subjects will be discharged from the study completely after the 6-week phone call.

### **9.7 Safety Monitoring**

The presence or absence of device related adverse events or complications, including epileptic seizures, occurring during the 72-hour SENSE monitoring period or emerging after the SENSE headset was removed (up to 7 days of hospital stay) will be documented.

A neurologist at the University of Cincinnati, who is not affiliated with the study or Sense Diagnostics, will serve as the independent safety monitor for this first-in-man study. The independent safety monitor will review adverse events and seizures for all subjects enrolled to detect any device related adverse events that may occur while the SENSE device is being worn or that emerged after exposure to the SENSE device. All adverse events, including seizures, determined to be device related will be recorded on the CRFs. The independent safety monitor will evaluate the incidence of seizures compared to the study stopping rules in Section 10.2 below to determine if early study termination is warranted.

### **9.8 Device Accountability**

All use of the SENSE device will be under the direct supervision of the principal investigator or his/her designee. Records of device accountability will be maintained for the study.

### **9.9 Early Withdrawal**

Subjects will be advised that they are free to withdraw from the study at any time. Subjects experiencing adverse safety events will be followed until the reaction has resolved. Appropriate supportive and/or definitive therapy will be administered as required. When a subject withdraws early from the study before completion of the 12 hour or 72 hour CT scan and SENSE measurement, or 6 week phone call, a final examination (including a final CT and SENSE measurement if before 72 hours) will be performed at the time of study withdrawal, whenever practicable.

### **9.10 Early Termination**

The investigator may discontinue a subject if a serious adverse event occurs and it is in the subject's best interest not to continue in the study, or if the subject has continuous EEG monitoring initiated, is prescribed a medication that in the investigator's best clinical judgment is known or suspected to lower the subject's seizure threshold, is discharged from the hospital, dies, or undergoes a neurosurgical procedure before study completion. Subjects who are discontinued from the study due to either the SENSE

device interfering with another device or another device (e.g., intraventricular catheter placement) interfering with the SENSE device should have the reason for discontinuation recorded as due to an adverse event. When a subject is terminated early from the study before completion of the 12 hour or 72 hour CT scan and SENSE measurement, a final examination (including a final CT and SENSE measurement) will be performed at the time of termination, whenever practicable, and the 72-hour end of monitoring adverse event assessment will be completed. The 7 day and 6 week adverse event assessments should also be completed whenever practicable.

## 10.0 Data Analysis and Statistical Considerations

A detailed statistical analysis plan (SAP) will not be developed for analysis of the data for this first-in-man study due to the small sample size of 10 subjects. Data from the study will be tabulated and summarized using descriptive statistics, where applicable, for safety and efficacy or to optimize the device design or aid in clinical trial design.

### 10.1 Sample Size Justification

The purpose of this first-in-man investigation is twofold: 1) to provide preliminary safety and effectiveness and device usage information that can be used to design the pivotal study to support the eventual marketing application for the SENSE device; and 2) to optimize the device design. Hence, the number of subjects suggested for this clinical investigation is not based on a statistical evaluation of any objective efficacy or safety outcome measures.

### 10.2 Stopping Rules

Consistent with usual procedures for the conduct of first-in-man studies, a priori specific guidelines are described below for stopping the study when the threshold for an excess number of safety events is reached. Stopping rules are based on the methods proposed by Moye.

The occurrence of seizures is the main adverse event of interest for this study. Seizures are defined as clinical tonic-clonic activity that occurs during the 72 hours of SENSE monitoring. Using the binomial observed event rate, the associated lower 90% confidence interval will be calculated for the observed event. The stopping decision is based on when the assumed true event rate, set at 16%, falls below the lower 90% confidence interval for the observed rate which is dependent upon the number of subjects accrued.

Using these parameters, the study is stopped if there are:

- 3 subjects with occurrence of seizure after SENSE monitoring within the first 6 subjects
- 4 subjects with occurrence of seizure after SENSE monitoring within the first 10 subjects

---

 Fundamentals for investigators. Lemuel A. Moyé, Springer, New York, 2003. No. of pages: xxiii+436.

The table below shows the observed event rate and the lower 90% confidence interval for that rate for the number of subjects enrolled at the stage when the allowed number of observed subjects with seizure changes. The allowed number of subjects with seizure is based on the assumed event rate, 16%, falling below the 90% CI for the observed rate as stated above.

Table: Seizure Threshold Rates for an Assumed True Event Rate of 16%

Subjects Enrolled	Number of Seizures (S)	Observed Event Rate	Lower 90% CI for Observed Event Rate
6	3	0.50	0.16
7	3	0.43	0.12
7	4	0.57	0.26
9	4	0.44	0.17
10	4	0.40	0.14
10	5	0.50	0.24

The total RF energy exposure for the SENSE device over the 72-hour testing period proposed in this clinical study (1 mW for ~302 minutes) is equivalent to the energy exposure from a 36-second cell phone call. Nevertheless, the rate of seizures was selected as the adverse event of interest due to theoretical concerns from limited animal studies in the published literature evaluating the impact of cell phone usage and seizure activity.

Cinar et al. studied the effects of electromagnetic waves (EMWs) on seizure activity in a mouse epilepsy model in which experimental groups of 10 mice were exposed to 900, 700, 500, 300 or 100 MHz EMWs for 20, 12, or 2 hours followed by intraperitoneal injection of pentylenetetrazole (PTZ) to induce seizures in all mice. Control group mice were injected with PTZ without exposure to EMWs. For the 900 MHz exposure (same as that used by the SENSE device), there were no significant differences between any of the experimental groups and PTZ-treated control at any exposure duration. Significant shortening of the initial seizure latency was observed at 500 MHz in the 2 hour exposure group, at 700 MHz in the 12 hour exposure group, and at 300 MHz in the 20 hour exposure group. No significant differences in the most severe seizure latency in any of the groups. The results of this study should be interpreted cautiously with respect to the SENSE device because: (1) the power level used in the study was not reported; (2) EMWs exposure without PTZ injection was not used as a control; (3) the sample size of mice studied (n = 10 mice) was too small to provide meaningful data; and, (4) the mice were exposed to 2 to 20 hours of continuous exposure, whereas the RF energy exposure

from the SENSE device is intermittent and with short durations (<1 minute per exposure).

Lopez-Martin et al. studied the effects of 2 hours of Global System for Mobiles (GSM)-modulated 900 MHz radiation (simulating cellular phone-type radiation) in a picrotoxin induced rat seizure model. Rats pre-treated with subconvulsive doses of picrotoxin and exposed to radiation suffered seizures and had increased cerebral levels of neuronal activity marker c-Fos. However, rats exposed to radiation but not pretreated with picrotoxin did not suffer seizures and cerebral c-Fos levels were significantly lower. From this, the authors concluded cellular phone type radiation could induce seizures in rats with a picrotoxin induced lowering of the seizure threshold but not in rats exposed to GSM-type radiation alone. Carballo-Quintas et al. reported similar results in picrotoxin treated rats exposed to 90 minutes, 24, or 72 hours of 900 MHz electromagnetic field.

Curcio et al. evaluated brain electroencephalogram (EEG) activity in 12 patients with focal epilepsy under acute real and sham exposure for 45 minutes of GSM-like electromagnetic fields in a double-blind crossover design. EEGs were obtained before, during, and after the GSM-like exposure. Observed EEG spiking activity (spike count) tended to be lower under real exposure than sham exposure. Acute GSM exposure resulted in slight changes in EEG quantitative indices without reaching any clinical relevance. From this experiment, the authors concluded there was no evidence of an increased risk of incoming seizures for these patients as a result of using mobile phones.

Based on the evaluation of the published literature and the *in vivo* porcine studies conducted by researchers from Sense Diagnostics, an increase in the rate of occurrence of seizures resulting from exposure to the SENSE device in this clinical study is unlikely, and any increase in the rate of seizures above that which is expected in this patient population would be a clinically significant adverse event that could warrant stopping the clinical trial, especially since study candidates with a history of seizure activity are excluded from the trial. Thus, in the absence of any human clinical experience with the SENSE device, the selection of seizures as the adverse event of interest is justified for this study based solely on the published literature.

---

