The SENSE device will be placed on the subject's head, and two small ink dots will be marked on the head corresponding to a known location on the device to allow for the device to be removed and replaced consistently throughout testing. After the 12-hour scan, monitoring may be performed continuously or intermittently. For continuous monitoring, the SENSE device will be set to scan every 10 minutes until the device is removed after completion of the SENSE measurement corresponding to the 72 hour CT scan. For continuous monitoring, the SENSE device will be worn for the entire 72 hour monitoring period except for any temporary suspensions. If the SENSE device is removed to perform the CT or SENSE monitoring is temporarily suspended, the SENSE device will be replaced; and SENSE monitoring will resume within 15 minutes, or as soon as practicable, after each CT scan. For intermittent monitoring, the SENSE device will be placed on the patient for a minimum of 22 minutes every 6 ( $\pm 1$ ) hours until the 72-hour CT scan is obtained. A final SENSE measurement will be completed within 15 minutes before or after the 72-hour CT scan. A SENSE measurement obtained within 15 minutes ~~of before or after~~ each CT scan, or as soon as practicable thereafter, will be used for comparison with the corresponding CT scan for data analysis.

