### 9.1 Study Duration

The study duration is a total of up to 8 weeks which includes up to 72 ( $\pm 12$ ) hours for SENSE device and CT scan monitoring, and a follow-up phone call at 6 ( $\pm 2$ ) weeks.

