### 9.3 SENSE Device Monitoring Procedure

The device will be used according to the written Instructions for Use provided by the Sponsor. The device will emit and analyze signals of 40 seconds once every 10 minutes for up to a maximum of 72 ( $\pm 12$ ) hours, effectively minimizing the amount of RF radiation to which the subject is exposed while providing essentially continuous monitoring from a clinical point of view. This corresponds to a duty cycle (DC) of about 7%.

If the subject's condition is such that a SENSE device measurement cannot be obtained, the measurement may be omitted at the investigator's discretion; and the omission should be documented in the source documents.

The user interface requires the researcher to input the subject ID and headset ID so that the results can be entered into a database either via upload or manually. The research personnel will also sync the headset with the control box. Once these steps are completed, the research personnel can activate the device by hitting "Start Monitoring." The software will provide error messages if any required fields are blank.

Once activated, the device scans the subject according to the schedule selected per protocol. Before each scan, the device will run a diagnostic to ensure that all components are functioning normally. Data will be collected after each scan for subsequent analysis and correlation with clinical and imaging data.

The processing control unit will store the results from each subject's scans in a file on the device. If the subject ID is changed, the device will start a new file.

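### The only numeric stopping rule carries conflicting counting windows: the definition counts seizures during monitoring, the stopping bullets count seizures after it

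*Combined protocol and SAP*

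**What the plan says.** Section 10.2 fixes the event first: "Seizures are defined as clinical tonic-clonic activity that occurs during the 72 hours of SENSE monitoring". Section 9.5.3 repeats it for the adverse events of particular interest: "defined as clinical tonic-clonic activity that occurs during the 72 hours of SENSE monitoring". The same section 10.2 then gives the operative rule, which stops the study at "3 subjects with occurrence of seizure after SENSE monitoring within the first 6 subjects" or at "4 subjects with occurrence of seizure after SENSE monitoring within the first 10 subjects". Neither bullet has an end time.

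Section 9.7 assigns the rule to the independent safety monitor. It has seizures documented during the monitoring period and also after headset removal, through at most seven inpatient days. It asks the monitor to review events in both periods and then to compare seizure incidence with section 10.2.

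On duration, section 9.3 says "The device will emit and analyze signals of 40 seconds once every 10 minutes for up to a maximum of" 72 (±12) hours, and section 9.1 gives the same allowance for "hours for SENSE device and CT scan monitoring". Section 7.0 keeps a continuously monitored subject on the device "until the device is removed after completion of the SENSE measurement corresponding to the 72 hour CT scan". Section 9.2 places that CT at 72 (±12) hours after the first study CT and lets monitoring begin before the first study CT if that scan is delayed. Section 10.0 says that no detailed SAP will be written, so no later analysis document is foreseen to settle the wording.

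**The concern.** A stopping rule needs one event definition with a start and an end. Here the definition and the trigger point in different directions. A seizure at 20 hours with the headset on meets the definition but not a literal reading of the bullets. A seizure on day 5, after removal, meets a literal reading of the bullets but not the definition. Section 9.7 puts both in front of the safety monitor and does not say which to count.

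This is the only numeric stopping rule in a first-in-man study, and its thresholds are small. One seizure classified the other way turns 3 of 6 (stop) into 2 of 6 (continue), or 4 of 10 into 3 of 10. Section 10.2 itself says that a seizure rate above expectation could justify stopping, so the person applying the rule should not have to choose the window after seeing the event.

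**Working it through.** **The wording side by side**

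| Place | Window for the seizure |
|---|---|
| 10.2 definition; 9.5.3 | during monitoring, described as 72 hours |
| 10.2, both bullets | after monitoring, no end |
| 9.7 | during monitoring and after removal (at most 7 inpatient days); which of these count is not stated |
| 9.1, 9.3 | no seizure window, but monitoring may run to 72 + 12 = 84 h |

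Nothing in the protocol says which wording prevails.

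**The 72 to 84 hour part.** If 72 hours is clock time, at most (84 − 72)/84 = 14.3% of the permitted period lies outside the definition, and none for a subject whose device is off by 72 h. Under the intermittent option the device need be on for only 22/360 = 6.1% of the time, so fewer device-on hours are affected.

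**The plan's own figures.** The threshold table in 10.2 reproduces with p − 1.645 × √(p(1 − p)/n):

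- 3/6: 0.164 (plan 0.16)
- 3/7: 0.121 (0.12)
- 4/7: 0.264 (0.26)
- 4/9: 0.172 (0.17)
- 4/10: 0.145 (0.14)
- 5/10: 0.240 (0.24)

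The table is not what is questioned here.

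**What the window does to the rule.** Inputs from 10.2 are the 16% assumed rate and the thresholds of 3 in the first 6 and 4 in the first 10. Two assumptions are added because the documents are silent: 16% is a 72-hour risk, and the hazard is constant. Then

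p(h) = 1 − 0.84^(h/72), which gives 0.135 at 60 h, 0.160 at 72 h and 0.184 at 84 h.

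P(stop) = P(X₆ ≥ 3) + Σ P(X₆ = x) × P(X₄ ≥ 4 − x) for x = 0, 1, 2, where X₆ and X₄ are the seizure counts in the first six and last four subjects.

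- All at 72 h: 0.0560 + 0.3513 × 0.0007 + 0.4015 × 0.0144 + 0.1912 × 0.1228 = 0.0855, or 8.6%.
- All at 84 h: 0.0803 + 0.2951 × 0.0011 + 0.3994 × 0.0215 + 0.2252 × 0.1568 = 0.1245, or 12.5% (0.12453 before rounding).
- Two of ten at 84 h, the rest at 72 h, averaged over enrolment order: 9.3%. Five of ten: 10.4%.
- All at 60 h: 5.4%.

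**The case against.** The strongest reply is that the intent is clear. Seventy-two hours serves mostly as a label: section 7.0 says "the SENSE device will be worn for the entire 72 hour monitoring period except for any temporary suspensions" although the scan that ends the period may fall at 60 or 84 hours, and section 9.10 asks for a 72-hour end-of-monitoring assessment even in subjects who stop early. On that reading the window ends when monitoring ends, and no device-on seizure is left out. Likewise, the bullets count seizures, a term already defined with its own window. Requiring the event to fall both during monitoring and after it would leave nothing to count, so *after* must mean after the start. Section 9.7 sends the safety monitor to the section where that definition stands.

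Most of this stands. The label reading is the likelier one, although section 4.0 does use 72 hours as clock time (72 × 60 × 0.07 = 302 minutes), and it makes the 72 to 84 hour part weak. The definition also makes a window during monitoring the probable intent. But the bullets still say the opposite, and section 9.7 explicitly brings seizures after removal into the monitor's review, so the contradiction has to be repaired by inference.

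Three stronger readings are tempting and should not be drawn:

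- A reader might infer that seizures between 72 and 84 hours escape oversight. They do not: sections 6.0, 9.7 and 10.6 have seizures recorded, reviewed and tabulated. Only their place in the count is unclear.
- A reader might combine the bullets with section 9.7 and conclude that the rule counts to 7 days. Under the same constant-hazard assumption that would give a risk of 1 − 0.84^(168/72) = 33.4% and a 48.7% chance of stopping with no device effect. No section says the count runs that long, the definition contradicts it, and a constant hazard over a week is unsupported.
- A reader might take this for an error in the plan's arithmetic. No stated figure is wrong on this account; it is a conflict of wording.

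**Conclusion.** The point holds as an inconsistency of definition in the study's only numeric stopping rule. The conflict between *during* and *after* applies to every subject and should be removed before the rule is used. The 72 versus 84 hour question is secondary: at most 14.3% of the permitted period, only for subjects monitored past 72 hours, and nil if 72 hours is a label. The documents give neither seizure timing nor how often monitoring passes 72 hours, so no probability that a decision would change can be stated. The stopping probabilities above are illustrations that depend on treating 16% as a 72-hour risk with constant hazard.

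**What to change.** - In 9.5.3 and 10.2, define the stopping-rule seizure as clinical tonic-clonic activity from first device activation to final headset removal, including intervals with the headset temporarily off for CT, suspension or intermittent monitoring. This also covers monitoring started before the first study CT.
- In both bullets, replace the *after* wording with: during SENSE monitoring as defined above.
- In 9.7, state that seizures after final removal are recorded and reviewed but do not count toward 3 of 6 or 4 of 10.

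These are wording changes that need no new data or procedures, and the thresholds can stay. The statistical cost, on the assumptions stated, is a rise in the no-effect chance of stopping from 8.6% to 9.3% if two of ten subjects run to 84 hours, and to at most 12.5% if all ten do. It would fall to 5.4% if every headset came off at 60 hours. The sponsor should state the period to which the 16% refers, so that this cost can be judged.

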## 8.0 Subject Population

This is a single site study that will be conducted at the University of Cincinnati Medical Center (Cincinnati, OH). Up to 10 subjects will be enrolled and receive a headset for monitoring.

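### The seizure stopping table in 10.2 uses an unnamed Wald limit at n = 6 to 10, and whether 3 of 6 meets the 16% criterion depends on a method and tail the protocol does not state

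*Combined protocol and SAP*

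**What the plan says.** Section 10.2 describes the calculation in one sentence: "Using the binomial observed event rate, the associated lower 90% confidence interval will be calculated for the observed event". The table is then explained this way: "The allowed number of subjects with seizure is based on the assumed event rate, 16%, falling below the 90% CI for the observed rate". Two triggers follow: "3 subjects with occurrence of seizure after SENSE monitoring within the first 6 subjects" and "4 subjects with occurrence of seizure after SENSE monitoring within the first 10 subjects".

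The table gives six rows of subjects, seizures and lower limit: 3/6, 0.16; 3/7, 0.12; 4/7, 0.26; 4/9, 0.17; 4/10, 0.14; 5/10, 0.24.

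Nothing in 10.2 says whether the limit is normal-approximation, exact or something else, or whether 90% refers to a two-sided interval (5% in the lower tail) or a one-sided bound (10%). The method is attributed to a textbook. Section 10.0 states that no detailed SAP will be written, so no other document fills the gap. Section 9.7 has the independent safety monitor compare seizure incidence with this section.

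**The concern.** An approximation that takes its standard error from the observed proportion is weak with 3 to 5 events in 6 to 10 subjects. If the first trigger clears the criterion only because of that approximation, the confidence attached to it is not what a reader would take from the text.

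This is the only numerical safety boundary in a first-in-human study. After a third seizure in six subjects, the safety monitor would hold a bullet that says stop, a printed limit that looks tied with 16%, and a standard exact calculation that may or may not agree, depending on an unstated tail.

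**Working it through.** **Inputs.** Assumed rate 0.16, the two triggers and the six rows, all from 10.2. Maximum sample size from 8.0: "Up to 10 subjects will be enrolled and receive a headset for monitoring".

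**Step 1: reproduce the printed column.** Wald limit = p − z·√(p(1−p)/n), with p = s/n. For 3/6 the standard error is √(0.25/6) = 0.2041, so the limit is 0.5 − 1.645 × 0.2041 = 0.1642, or 0.1632 with z = 1.65. For 4/10 the standard error is 0.1549, giving 0.1452 with z = 1.645 and 0.1444 with z = 1.65. With z = 1.65 all six rows match the print; with 1.645 five do, since 4/10 would round to 0.15. A one-sided 90% Wald limit (z = 1.282) gives 0.238 for 3/6 and does not match. The continuity-corrected, Wilson, Jeffreys, mid-P and exact limits do not reproduce the column either. The column is therefore Wald, with a 5% lower tail.

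**Step 2: exact limits.** The Clopper-Pearson lower limit is the rate at which P(X ≥ s) equals the tail α, i.e. the α quantile of Beta(s, n−s+1). It exceeds 0.16 exactly when P(X ≥ s | n, 0.16) < α. For 3/6:

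P(X ≥ 3) = 1 − 0.84⁶ − 6(0.16)(0.84⁵) − 15(0.16²)(0.84⁴) = 1 − 0.3513 − 0.4015 − 0.1912 = 0.056.

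This is above 0.05 and below 0.10, so 3/6 fails at a 5% tail and clears at a 10% tail.

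| Row | Printed | Wald, z = 1.645 | P(X ≥ s) at 16% | Exact, 5% tail | Exact, 10% tail |
|---|---|---|---|---|---|
| 3/6 | 0.16 | 0.164 | 0.056 | 0.153 | 0.201 |
| 3/7 | 0.12 | 0.121 | 0.087 | 0.129 | 0.170 |
| 4/7 | 0.26 | 0.264 | 0.015 | 0.225 | 0.279 |
| 4/9 | 0.17 | 0.172 | 0.042 | 0.169 | 0.210 |
| 4/10 | 0.14 | 0.145 | 0.061 | 0.150 | 0.188 |
| 5/10 | 0.24 | 0.240 | 0.013 | 0.222 | 0.267 |

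At the 5% tail only 3/6 changes side of 16% when Wald is replaced by exact. At the 10% tail every row clears 16%, including 3/7, which the bullets let continue. Neither exact version reproduces the bullets.

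**Step 3: effect on stopping.** Stops are counted from three seizures up, checking after each subject, so that the rules are compared on the same footing. The tables imply these boundaries:

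- Wald: 3 within 6, or 4 within 9.
- Exact 5% tail: 3 within 5, or 4 within 9.
- Bullets: 3 within 6, or 4 within 10.

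For Wald at 16%, add P(3 or more in 6) to the paths that reach 4 by subject 9:

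0.0560 + P(2 in 6) × P(2 or more in 3) + P(1 in 6) × P(3 in 3) = 0.0560 + 0.1912 × 0.0686 + 0.4015 × 0.0041 = 0.071.

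For exact 5% tail at 16%:

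P(3 or more in 5) + P(2 in 5) × P(2 or more in 4) + P(1 in 5) × P(3 or more in 4) + P(0 in 5) × P(4 in 4) = 0.0318 + 0.1517 × 0.1228 + 0.3983 × 0.0144 + 0.4182 × 0.0007 = 0.056.

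The same sums at 32%, an illustrative doubling of the assumed rate, complete the comparison:

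| Rule | P(stop) at 16% | P(stop) at 32% |
|---|---|---|
| Wald, from three seizures | 7.1% | 38% |
| Exact 5% tail, from three seizures | 5.6% | 35% |
| Bullets as written | 8.6% | 45% |

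The bullets differ from the Wald row only by the stop at 4 of 10, which is a separate conflict: the printed limit there is 0.14, below 16%.

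**The case against.** A reader might infer that the first trigger fails the protocol's own criterion. The documents do not support that. Section 10.2 never commits to an exact interval, and on the method the table evidently uses, 3/6 gives 0.163 to 0.164, which is above 0.16. It fails only if one substitutes Clopper-Pearson and also fixes a 5% tail. Clopper-Pearson is conservative, and other small-sample limits keep the trigger: Wilson 0.221, Jeffreys 0.209, mid-P 0.189, exact 10% tail 0.201.

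Nor does the approximation make the first trigger too lax. Relative to the exact 5% tail it stops earlier, at 3 rather than 4 of 6. Section 10.2 describes the rules as guidelines, an independent monitor reviews every seizure, and the study is otherwise descriptive. The printed numbers do imply a 5% tail, even though the words do not say so, and the cited textbook may specify the method.

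All of this stands, and it limits the size of the point. It does not remove it. The Wald limit departs from the exact limit in both directions (4/7: 0.264 against 0.225; 3/7: 0.121 against 0.129), the method and tail are not in the protocol, and the status of the first trigger changes with them.

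**Conclusion.** The concern holds in this form: the lower-limit column is an unnamed Wald limit, unreliable at these sample sizes, and 3 of 6 meets the stated criterion or not according to a method and tail that the protocol leaves open. At the table's implied 5% tail, moving to exact limits changes the side of 16% for one row of six.

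The effect on operating characteristics is modest: 1.5 percentage points at a true rate of 16% (7.1% to 5.6%) and about 3 at 32% (38% to 35%). It would be tempting to quote the gap between the bullets (8.6% / 45%) and the exact rule as the cost of the approximation, but part of that gap comes from the 4-of-10 conflict and not from the interval method.

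These figures assume independent subjects with a common seizure rate, a check after each subject, all 10 subjects enrolled unless stopped, and no stop before a third seizure. Severity is moderate: the section should be corrected, but the finding does not show the boundary to be unsafe.

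**What to change.** In 10.2, recompute the column with a small-sample binomial limit, for example exact Clopper-Pearson, and print it to three decimals so that no row appears tied with 16%. Add a sentence naming the method and the tail. Then reconcile both bullets and every table row with the recomputed column: at a 5% tail this affects 3/6 and 4/10, and at a 10% tail it affects 3/7. Beside the table, state the probability of stopping at 16% and at one higher rate.

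The sponsor and the safety monitor must choose the tail and the boundary; this review does not. The cost is one table and one or two sentences, plus whichever trigger or stated confidence level has to move so that text, bullets and table agree.
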